27 DEC 2017

Controlled Study of the Effect of a Medical Food
Containing All Three Macular Carotenoids and Essential Cofactors
Compared to AREDS2 on Early Macular Degeneration

PURPOSE:

This 6-month randomized control study is undertaken to compare the effect of treatment with LumegaZ, a medical food containing lutein, zeaxanthin, and meso-zeaxanthin, as well as essential cofactors, other antioxidants, and mitochondrial support, with the effect of treatment with AREDS2. Patients with early macular degeneration, defined as photographically visible drusen with or without abnormal dark adaptation on the AdaptDx will be randomized 2:1 and both groups will be compared to untreated patients with normal dark adaptation.

BACKGROUND:

Macular degeneration is the most common cause of blindness in people over the age of 60. The incidence of macular degeneration at all stages is 1 in 8 and is more common than diabetes and glaucoma at the same age.

The dietary carotenoids lutein and zeaxanthin (derived primarily from leafy green vegetables and other colored fruits and vegetables) as well as meso-zeaxanthin, a metabolite of lutein, are stored in the macula in all healthy retinas. This area serves central vision, and is the specific area that is affected by macular degeneration. The accumulation of these pigments results in a yellowish coloration of the retina, the concentration of which is called macular pigment density. A large multicenter trial called AREDS 2 (2013) showed that supplementing lutein and zeaxanthin reduced progression of moderate to advanced AMD by 25%. The CREST (2014) and MOST (2015) studies showed that supplementation of all 3 macular pigments resulted in normalization of the macular pigment profile and improvement in contrast sensitivity in early AMD. All 3 macular carotenoids are recognized by the FDA as 'generally regarded as safe (GRAS) for supplementation in foods.

Macular degeneration can be understood as a disease of excessive oxidation of the retinal tissue with genetic, age, dietary and light exposure components leading to accumulation of oxidized cholesterol and polyunsaturated fatty acids both on Bruch's membrane and between Bruch's membrane and the retinal pigment epithelium in a condition analogous to plaque

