buildup in arteries. These deposits block transfer of waste out of the retina leading to more accumulation and block transfer of nutrients into the retina. In macular degeneration, not enough Vitamin A crosses Bruch's membrane because of the build-up, causing a localized deficiency of Retinol in the parafoveal rods. This causes slower dark adaptation after bleaching light, which is the earliest symptom of macular degeneration: difficulty driving in darkness or adapting to dark conditions increasing with aging.

Abnormal dark adaptation found by AdaptDX testing is the earliest clinical sign of macular degeneration. This has enabled diagnosis of subclinical macular degeneration with 90% positive and negative test reliability, 3-5 years before the first drusen is visible clinically. Those patients who exhibit impaired dark adaptation, whether they are subclinical with no drusen or early with mild drusen, may benefit from nutritional and /or lifestyle changes which could significantly slow the progression of the disease. This would result in maintenance of retinal health and visual performance.

It is clear that early, effective intervention in any disease process is the key to reducing morbidity. Earlier diagnosis of macular degeneration is now possible with AdaptDX testing. Effective intervention involves reducing the photo-oxidative damage of the retina caused by the visual process in the retina, and potential clearing of the early stage blockage of bidirectional transport across Bruch's membrane. Thirty percent of people over age 60 have abnormal dark adaptation. Likewise, 30% of people have an abnormal spatial profile of macular pigment indicating insufficient meso-zeaxanthin creation from lutein. Supplementing meso-zeaxanthin as well as lutein and zeaxanthin can restore the macular pigment spatial profile and improve visual performance in early macular degeneration. Early results from an as yet unpublished exploratory study in progress with such supplementation in subclinical AMD indicate improvement in MPOD and best corrected contrast sensitivity in many patients by 6 months.

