A medical food is a special category of supplement approval by the FDA where physicians prescribe it for nutritional treatment of specific medical conditions. The medical food to be used by patients in this study contains not only all the macular carotenoids in micelle formulation for improved absorption, but also significant cofactors, such as vitamins, minerals, ALA, astaxanthin, N-acetylcysteine, carnosine and others. All of these ingredients working together should significantly improve the mitochondrial, antioxidant and anti-inflammatory functions of the retina. This should allow creation of less damage to critical elements of the retina and less toxic waste such as oxidized cholesterol and oxidized polyunsaturated fatty acids which are the major components of the sub-RPE and Bruch's membrane deposits. This controlled study will attempt to show that using a medical food designed to optimize retinal metabolism and antioxidant capacity will exert a positive effect in subclinical macular degeneration, which is greater than supplementation with AREDS2 and will also improve measured functions into the range of function in untreated normal patients.

STUDY:

All study candidates are routine patients in a general ophthalmology practice. All patients who are interested will be offered the opportunity to participate in this controlled study of the effect of a nutritional food on subclinical macular degeneration. Each patient will undergo a screening AdaptDx to separate patients with normal dark adaptation from those with abnormal dark adaptation. All patients will receive the same exams at baseline, 3 months and 6 months. For details, see the listing below. Those who are confirmed as normal with extended dark adaptation testing will receive no treatment precisely because they are defined as not having a problem needing this treatment. Those who are confirmed with early macular degeneration by photographically visible drusen and have dark adaptation scores of less than 10 minutes will receive treatment by ingesting a commercially available medical food, containing all 3 macular pigment as well as essential cofactors and other antioxidants, or AREDS2, randomized 2:1 for 6 months. If positive effects are noted, it is possible that the study might be extended. The tasks below are part of standard diagnostic clinical eyecare practice.

- Baseline, 3 month and 6 month examinations
 - History
 - Risk factors
 - Best corrected visual acuity

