 - Best corrected contrast sensitivity (CSV 1000)
 - Intraocular pressure, nondilated slit-lamp exam
 - Dark adaptation (AdaptDX, extended exam)
 - Macular pigment optical density (MapcatSF)
 - Macular ocular coherence tomography (Zeiss Cirrus OCT)
 - Fundus photography (Zeiss VisuCam Pro)

Because these patients will have additional problems found in routine clinical practice, other exams may occur for other problems and will not be considered part of the study data. Should any adverse effects be noted thought to be from the study treatment, the patient will be examined to understand the effect and if it is felt to be not significant, the patient will be asked to continue in the study. In the highly unlikely event a serious adverse effect is noted the patient will be terminated from the study and appropriate treatment will be undertaken.

DATA COLLECTION:

The data will be maintained on standardized forms and printable graphics, as well as in the patient's routine clinical file. To protect identifiable information, files will be locked in a file cabinet, accessible only the PI and the study coordinator. Data will be transcribed without

personally identifiable information into standard Excel files and analyzed as appropriate using standard statistical techniques.

STUDY REQUIREMENTS:

This study will be conducted with the protocol, good clinical practices and applicable regulatory requirements. This is a no significant risk study, using commercially available supplements, Lumega-Z or AREDS2, containing 2 or 3 of the three carotenoids that are FDA “generally recognized as safe” for food supplementation and are found in all healthy retinas. All examinations are noninvasive and are performed with FDA cleared, commercially available medical devices in routine clinical use.

The study population consists of 90 male and female patients in a routine clinical practice age 60 and over who have early macular degeneration as defined as a few drusen visible on Visucam and have an AdaptDx score less than or equal to 10 minutes. No vulnerable populations will be studied.

The patient will be studied for improvements in ocular function. Primary endpoints would be improvement in macular pigment optical density long form, improvement in best corrected contrast sensitivity and improvement in best corrected vision. Secondary endpoints would be improvement of AdaptDx long form time or a reduction in drusen.

The study supplements for each

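### The untreated normals have no stated age limit and no age adjustment is named, so the comparison of treated patients' function with the normal range is open to confounding by age

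*Combined protocol and SAP*

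**What the plan says.** **Population.** Study Requirements states: "The study population consists of 90 male and female patients in a routine clinical practice age 60 and over who have early macular degeneration". The same sentence continues with the disease definition, "as defined as a few drusen visible on Visucam and have an AdaptDx score less than or equal to 10 minutes". No other age limit or patient count for the study appears in the available text.

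**Reference group.** The Purpose says that the patients with early disease "will be randomized 2:1 and both groups will be compared to untreated patients with normal dark adaptation". The last paragraph of the Background makes this comparison part of the aim: treatment is expected to beat AREDS2 and "will also improve measured functions into the range of function in untreated normal patients".

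**Entry of normals.** The Study section gives their source, "All study candidates are routine patients in a general ophthalmology practice", and their one condition: "Those who are confirmed as normal with extended dark adaptation testing will receive no treatment". It gives no age range, number or matching rule.

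**Age and function.** The Background describes the earliest symptom of macular degeneration as "difficulty driving in darkness or adapting to dark conditions increasing with aging", and puts abnormal dark adaptation at 30% of people over 60.

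**Analysis.** The statistical analysis text at the end of the combined document says that the analysts receive age and sex. It names a mixed-design ANOVA over three time-points and paired t-tests as possible methods. It does not mention age as a covariate, a stratification factor or a matching variable.

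**The concern.** The treated arms are fixed at 60 and over. The group that sets their target is not. A normal without drusen does not meet the definition attached to the 90, so neither the age limit nor the count reaches that person. A patient well below 60 who passes extended dark adaptation testing could be enrolled as a normal without any deviation from the protocol.

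If that happened often enough to pull the group's age down, the normal range would reflect youth as well as absence of disease. A treatment that restored function to what is usual at the patient's own age could still fall short of it. The reference comparison is not randomised, so design and adjustment are its only protection against this, and the plan specifies neither for age.

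**Working it through.** **1. Does the age limit reach the normals?** Set the three definitions side by side:
- Study Requirements: aged 60 and over, with early macular degeneration, a few drusen, and an AdaptDx score at or below 10 minutes. The 90 and the age limit belong to this group.
- Study section: normals are those confirmed normal on extended dark adaptation testing. They are routine patients of the practice and receive no treatment.
- Purpose: early disease means visible drusen, with or without abnormal dark adaptation.

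The age limit and the count are attached only to the first group. The definitions also overlap. No available text requires normals to be free of drusen, so a patient with drusen and normal dark adaptation fits the Purpose's definition of early disease and also the Study section's definition of an untreated normal.

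**2. The plan's own figure.** As worded, all 90 have early disease. A 2:1 allocation gives 90 × 2/3 = 60 and 90 × 1/3 = 30. The number of normals is then unstated. The 90 itself cannot be reproduced, because the documents give no significance level, power, effect size, SD or dropout rate.

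**3. Which comparisons carry an age offset?** Suppose that younger age raises the normals' mean by a constant δ at every visit.
- Lumega-Z versus AREDS2: both arms are randomised from one population aged 60 and over, and δ does not enter.
- Change from baseline, treated versus normals: the normals' change is (μ₆ + δ) − (μ₀ + δ) = μ₆ − μ₀, so δ cancels. The group-by-time term of a mixed ANOVA is free of δ for the same reason. Only a difference in the rate of change with age over six months would remain.
- Level at a visit, treated versus normals, and the between-group main effect of the ANOVA: δ stays in full.

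The exposed comparison is therefore the one of levels, which is the one that the normal-range aim needs.

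**4. How large could δ be?** The documents give no slope of function on age and no ages for the normals. Both inputs below are assumptions. Shift in SD = (age gap in years ÷ 10) × slope per decade.

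| Age gap | 0.1 SD/decade | 0.2 | 0.3 | 0.4 |
|---|---|---|---|---|
| 5 years | 0.05 | 0.10 | 0.15 | 0.20 |
| 10 years | 0.10 | 0.20 | 0.30 | 0.40 |
| 15 years | 0.15 | 0.30 | 0.45 | 0.60 |

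For scale, take 60 Lumega-Z patients and an assumed 30 normals. The standard error of a difference in means is √(1/60 + 1/30) = 0.224 SD. The shift is then 0.05/0.224 = 0.2 to 0.60/0.224 = 2.7 standard errors. This yardstick is rough, because the aim refers to a range and not to a mean. The table applies only to measures that worsen with age. The documents do not say that macular pigment optical density, the first primary endpoint listed, is one of them.

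**5. Would a common limit be enough?** Not by itself. If normal adaptation becomes less common with age, selecting on a normal result can leave the normals younger even among those over 60. A covariate alone is also weak if many normals lie below 60, because the adjustment would then extrapolate outside the treated arms' ages. The limit secures overlap and the covariate deals with the remaining gap.

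**The case against.** **The normals may not be younger.** A reader might infer that selecting on normal dark adaptation will produce a younger group. The documents do not show this. The Background attributes slow adaptation to macular degeneration and gives no rate of decline in healthy people. Its 30% abnormal over age 60 leaves about 70% not abnormal, so older normals should be easy to find in the same practice. A younger group is permitted, not predicted.

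**The limit may have been meant for everyone.** The sentence speaks of the study population, so the authors may have intended 60 and over throughout. That is plausible, and nothing suggests a decision to admit younger normals. It does not settle the matter, because the same sentence restricts that population to early disease and so would shut out the drusen-free normals whom the Purpose requires. Some pages, including consent pages, were not available, so the finding covers the available text only.

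**The main results are safe.** This stands. The primary endpoints are worded as improvements, and the randomised contrast carries no age offset. Nor can one say that missing the normal range would be read as lack of effect, because superiority over AREDS2 is stated as a separate aim.

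**Age adjustment is not excluded.** The analysis methods are listed as possibilities and age is supplied. That is correct: adjustment is unspecified, not ruled out. It still leaves the choice to be made after the data are seen.

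**The count of 90.** A reader might also infer that the randomised arms are smaller than 60 and 30 because the 90 includes normals. The wording does not support that. It needs a clear statement, but it is separate from age bias.

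**Conclusion.** The concern holds in a limited form. In the available text, the age limit of 60 and the count of 90 apply only to patients with early macular degeneration. The untreated normals have no stated age limit, and no age adjustment is named. The plan therefore allows confounding by age in one place: the secondary, non-randomised comparison of treated patients' level of function with that of normals.

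Whether bias would occur, and how much, cannot be known from the documents. The range of about 0.05 to 0.6 SD rests entirely on the assumed slopes and age gaps. At the low end it would be negligible. At the high end it could decide whether treated patients appear to reach the normal range. The remedy is worth making because it uses the protocol's own age limit and a variable that the analysts already receive.

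**What to change.** 1. In Study Requirements, apply the existing limit of 60 and over to the untreated normals as well as to the randomised patients.
2. In the same sentence, state whether the 90 includes the normals. If it does, give the randomised number; if not, give the number of normals separately.
3. In the statistical analysis text, pre-specify age as a covariate in every comparison of levels with the normals.
4. Reconcile the Purpose, the Study section and Study Requirements so that a patient with drusen and normal dark adaptation falls in only one group. The protocol's authors must decide which group.

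The cost is a few sentences and one covariate already in the transferred data. The downside is that younger volunteers could no longer serve as normals, so that group may fill slightly more slowly.

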At the end of the trial period, data will be collected by the Principal Investigator and analyzed by professional optical engineers at Western University of Health Sciences, Pomona CA. The data provided will only contain patient ID, age, and sex, without containing any identifying details about each participant. Data will be analyzed upon measurement quality, according to the respective manufacturer procedures, in each outcome measure. In the event which data is missing or incomplete, we will evaluate the appropriate measures to include the available information and consult with qualified professionals.

Preliminary and sub-analyses will be performed using the statistical programming software, SPSS Systems. The objective is to examine the distribution and potential relationships within data sets through standardized descriptive-numerical summaries. Statistical analysis strategies may include a mixed-design Analysis Of Variance (ANOVA) to examine the following outcome measures across the three time-points of data collection; including visual acuity, contrast sensitivity, dark adaptation recovery, and MPOD levels. A post hoc sub-analysis of paired sample t-test may be used (either Bonferroni correction or Tukey test) to evaluate the change in each outcome measure parameter, if needed, in respect to each treatment group. Additionally, each group-measurement may be separated and analyzed by eye; to evaluate inter-eye differences from each treatment. Results of the statistical analysis will be analyzed as group averages of each outcome measurement.

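### If patients with normal dark adaptation are randomised, a whole-arm average of AdaptDx time shrinks any Lumega-Z versus AREDS2 effect confined to impaired patients, and the plan names no baseline-adjusted or abnormal-at-baseline analysis

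*Combined protocol and SAP*

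**What the plan says.** **Endpoint.** STUDY REQUIREMENTS states: "Secondary endpoints would be improvement of AdaptDx long form time or a reduction in drusen". BACKGROUND explains that the disease slows dark adaptation, so improvement means a shorter time.

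**Who is randomised.** PURPOSE takes patients with "photographically visible drusen with or without abnormal dark adaptation on the AdaptDx will be randomized 2:1". STUDY says something different: "Those who are confirmed as normal with extended dark adaptation testing will receive no treatment". It also says that treatment goes to those with "photographically visible drusen and have dark adaptation scores of less than 10 minutes will receive treatment". STUDY REQUIREMENTS describes 90 patients with early macular degeneration who "have an AdaptDx score less than or equal to 10 minutes". Both numeric limits are upper limits; neither section gives a lower one.

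**Analysis.** The unheaded statistical text at the end of the combined document lists dark adaptation among the outcomes. A mixed-design ANOVA over three time-points may be used for it. The text then says: "Results of the statistical analysis will be analyzed as group averages of each outcome measurement". Baseline enters only as one of the three time-points. The text names no adjustment for baseline AdaptDx time, no stratum and no analysis set defined by baseline dark adaptation.

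**The concern.** An endpoint worded as improvement needs a deficit that can shrink. STUDY says of patients with normal dark adaptation that they "will receive no treatment precisely because they are defined as not having a problem needing this treatment", and the protocol's aim is to bring function into the range seen in untreated normal patients. On AdaptDx time, a randomised patient already in that range has little or nothing to gain.

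If such patients sit in both arms and the arms are compared by their means, a real shortening in impaired patients is averaged with near-zero change in the others. A null result could then mean that the product does nothing for dark adaptation, or that too few patients had a deficit. The protocol calls abnormal dark adaptation the earliest clinical sign of the disease and ties it to the mechanism the product is meant to act on, so the ambiguity would fall on an informative functional measure.

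**Working it through.** The plan states no alpha, power, effect size, SD or expected share of normals, so it has no figure of its own to reproduce. What follows is illustrative.

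**Inputs from the documents**
- 90 patients (STUDY REQUIREMENTS) and 2:1 allocation (PURPOSE, STUDY). This gives 60 versus 30 if all 90 are randomised.

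**Assumptions**
- Two-sided alpha 0.05, normal approximation.
- Share p of each arm abnormal at baseline. Effect d = 0.8 SD in abnormal patients and zero in the rest.
- SD of the baseline-adjusted outcome is 1 in abnormal patients and r in normal patients.
- BACKGROUND gives 30% abnormal, but for people over 60 in general, not for patients with drusen. So p is varied.

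**Step 1. Size of the averaged effect.** It equals p × d. At p = 0.5 it is 0.5 × 0.8 = 0.40. This does not depend on r.

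**Step 2. Abnormal patients only.** SE = sqrt(1/(60p) + 1/(30p)). At p = 0.5, SE = sqrt(1/30 + 1/15) = 0.316, z = 0.8/0.316 = 2.53, and power is 72%.

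**Step 3. All randomised, equal SDs (r = 1).** SE = sqrt(1/60 + 1/30) = 0.224. At p = 0.5, z = 0.40/0.224 = 1.79 and power is 43%. The ratio of the two z values is 1/sqrt(p): 1.83, 1.41, 1.20 and 1.05 at p = 0.3, 0.5, 0.7 and 0.9.

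**Step 4. All randomised, smaller SD in normals.** Let V = p + (1 − p)r². An effect present in only some patients also adds p(1 − p)d² to the variance in the Lumega-Z arm. So SE = sqrt((V + p(1 − p)d²)/60 + V/30). At p = 0.5 the added term is 0.25 × 0.64 = 0.16.
- r = 1: SE = sqrt(1.16/60 + 1/30) = 0.230, z = 1.74, power 41%. Step 3 omits the added term, hence its 43%.
- r = 0.5: V = 0.625, SE = sqrt(0.785/60 + 0.625/30) = 0.184, z = 2.17, power 58%.
- r = 0.25: V = 0.531, SE = sqrt(0.691/60 + 0.531/30) = 0.171, z = 2.34, power 65%.

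| p | Abnormal only | All, r = 1 | All, r = 0.5 | All, r = 0.25 |
|---|---|---|---|---|
| 0.5 | 72% | 41% (43% by Step 3) | 58% | 65% |
| 0.7 | 85% | 69% (71% by Step 3) | 79% | 82% |
| 1 | 95% | 95% | 95% | 95% |

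**Step 5. How much could normals gain before restriction stops helping?** With equal SDs and an effect of k × d in normals, the whole-arm effect is (p + (1 − p)k)d. Ignoring the added variance term, its z matches the abnormal-only z when k = (sqrt(p) − p)/(1 − p). That is 0.41 at p = 0.5 and 0.46 at p = 0.7.

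**The case against.** **The dilution may not arise at all.** If the STUDY rule that confirmed normals go untreated overrides PURPOSE, p = 1 and both analyses coincide. This objection stands. The documents do not say which statement governs, so the point is conditional.

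**The power loss depends on the SD in normals.** Short times near a floor may vary less. If so, these patients add little noise, and the gap narrows from about 30 points to 7 at p = 0.5. This stands too. A reader might take 43% versus 72% as the cost; it is the equal-SD case, and the documents give no SD to support it. The shrinkage of the mean by p is unaffected.

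**Zero effect in normals is an assumption.** The STUDY remark about having no problem describes the untreated comparison group. A patient with drusen and normal dark adaptation still has early disease under PURPOSE, and a difference could arise if AREDS2 patients worsened. This partly stands, and Step 5 shows how large such an effect would need to be.

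**The plan does not commit to pooling.** A reader might infer that all randomised patients must be averaged together. The statistical text defines no analysis population, says ANOVA may be used and allows for sub-analyses. The supportable criticism is that the dark-adaptation analysis set and baseline adjustment are unspecified.

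**The 10-minute limit is a different matter.** A reader might blame it for the dilution. It excludes the longest times and so restricts the range, but it may also lower the SD. It is not a cause of dilution.

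**Conclusion.** The point holds in conditional form. If patients with normal dark adaptation are randomised, as PURPOSE states, a whole-arm mean of AdaptDx time multiplies any effect confined to impaired patients by p. The plan specifies nothing that would reveal this.

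The consequence for power is a range. At p = 0.5, under the assumptions above, all-randomised power is roughly 41–43%, 58% or 65% for a normal-to-abnormal SD ratio of 1, 0.5 or 0.25, against 72% in abnormal patients alone. At p = 1 there is no loss. These figures assume all 90 patients are randomised, 0.8 SD in abnormal patients and no effect in the rest.

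A reader might go further and make the abnormal subgroup the endpoint itself. The documents do not support that: they give no cut-off to define the subgroup, and restriction is a debatable trade-off if normals can also benefit. The primary endpoints and the drusen endpoint are untouched by this argument. Priority is optional to moderate.

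**What to change.** 1. Reconcile PURPOSE, STUDY and STUDY REQUIREMENTS on whether patients with drusen and normal dark adaptation are randomised.
2. Keep the all-randomised Lumega-Z minus AREDS2 difference in 6-month extended AdaptDx time as the analysis of this secondary endpoint, adjusted for baseline extended time.
3. Prespecify beside it the same baseline-adjusted difference in patients abnormal on the baseline extended test. Use the normal/abnormal classification the site already makes, and write its cut-off down before analysis. The only AdaptDx number now in the protocol is the entry limit. Report the number abnormal in each arm.
4. State that a null all-randomised result alone will not be read as no effect on dark adaptation.

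**Cost.** This needs a few sentences of analysis text and a written cut-off. The extended test is already done at baseline, 3 and 6 months, so no new data are needed. The abnormal-only estimate is less precise. At p = 0.5 it rests on about 30 versus 15 patients, with a 95% half-width of 1.96 × 0.316 = 0.62 SD, against 1.96 × 0.224 = 0.44 SD for all 90 with equal SDs. If only abnormal patients turn out to be randomised, items 2 and 3 give the same result and nothing is lost.
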